### Efficacy Analyses

The efficacy endpoints will be analyzed on the Intent-to-Treat-infected (ITT-i) Set, consisting of all subjects who were randomized, treated and had a confirmed influenza A infection, and will be analyzed by randomized treatment.

Descriptive statistics will be used for all efficacy endpoints and will be tabulated by treatment arm and stratification factors (type of baseline SOC and time since onset of symptoms).

Subgroup analyses will be performed by, but might not be limited to, region and age group.

As a confirmatory strategy, to account for multiplicity in the statistical evaluation of the most important efficacy endpoints, hierarchical testing will be applied to control for overall Type I error. The following endpoints are included in the confirmatory strategy:

1. Time to resolution of the 7 primary influenza-related symptoms (cough, sore throat, headache, nasal congestion, feeling feverish, body aches and pains, fatigue), ie, primary endpoint
2. Incidence of complications associated with influenza after the start of study treatment
3. Hospital admission rates 28 days after treatment initiation

First, the primary endpoint will be tested for superiority of pimodivir in combination with SOC over placebo in combination with SOC at the 2-sided 5% significance level. If superiority is shown on the primary endpoint, the first secondary endpoint in the sequence as indicated above will be tested for superiority at the same significance level. If superiority is shown for this secondary endpoint, the second (and last) secondary endpoint in sequence will be tested. In case superiority is not shown for an endpoint, no further endpoints in the sequence will be tested for superiority. For the primary endpoint, the results from the Gehan-Wilcoxon test will be used in the hypothesis testing. For the secondary endpoints, incidence of complications associated with influenza after the start of study treatment and hospital admission rates 28 days after treatment initiation, the results of the logistic regression will be used.

### ***Primary Endpoint***

Time to resolution of the 7 primary influenza-related symptoms is defined as the time from initiation of study treatment to when all symptoms are considered resolved for at least 24 hours. A symptom is considered resolved, depending on pre-existence of the symptom:

- The symptom is pre-existing:
  - The symptom is considered resolved if post-baseline severity is equal or lower than the pre-existing severity
- The symptom is not pre-existing:
  - The symptom is considered resolved if its severity is scored at most mild post-baseline

The primary efficacy analysis of the time to resolution of the 7 primary influenza-related symptoms (cough, sore throat, headache, nasal congestion, feeling feverish, body aches and pains, fatigue) will consist of a stratified Gehan-Wilcoxon test (using the randomization stratification factors, ie, type of baseline SOC and time since onset of symptoms as strata). Kaplan-Meier curves, overall and by stratum, and a stratified log-rank test for time to symptom resolution will also be provided. Additionally, the data will be analyzed using an accelerated failure time model. Also, a Cox proportional hazards model will be applied. Both models will be adjusted for stratification factors and baseline symptom domain score.

### ***Secondary Endpoints***

The incidence of hospital admissions 28 days after treatment initiation will be analyzed using a logistic regression. Stratification factors will be added as covariates to the model.

Return to daily activities will be assessed once daily by means of the question 'Over the past 24 hours, how much has influenza (flu) interfered with your ability to carry out your daily activities?' The responses will be dichotomized: 'Not at all' and 'A little bit' will be considered as returned to daily activities and 'Somewhat', 'Quite a Bit' and 'Very much' will be considered as not having returned to daily activities. "Time to return to daily activities" is defined as the time from initiation of study treatment to when return

to daily activities is reached for at least 24 hours. This endpoint will be analyzed analogously to the primary endpoint.

Time to resolution of fever will be analyzed analogously to the primary endpoint.

The incidence of treatment-emergent adjudicated complications will be analyzed using a logistic regression. Stratification factors will be added as covariates to the model.

The time to viral negativity, by qRT-PCR and viral culture, will be analyzed analogously to the primary endpoint. The viral load over time will be analyzed using mixed effects modeling. Stratification factors will be added as covariates to the model. Additional predictive baseline covariates may be added.

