5.2.2. Estimand

The population of interest is adolescent, adult, and elderly non-hospitalized subjects with a confirmed influenza A infection who are at risk of developing complications.

The primary variable of interest is the time to resolution (in hours) of the 7 primary influenza-related symptoms (cough, sore throat, headache, nasal congestion, feeling feverish, body aches and pains, fatigue). Resolution is achieved if all 7 symptoms are scored as none or mild, or, are equal to or lower than the pre-influenza severity for 24 hours expressed in 3 successive recordings or 4 successive recordings where 1 in between missing recording is allowed.

The intercurrent event of use of SOC is handled in a treatment policy strategy as the primary endpoint is derived in the same way irrespective of the components of SOC, that could include influenza antivirals. For missing recordings, the composite strategy is applied. Missing recordings due to death or hospitalization are covered by using the maximum time over all subjects as the censored resolution time. Additionally, 1 missing datapoint, not due to death or hospitalization is allowed in the definition of resolution. When multiple missing recordings, not due to death or hospitalization, prevent the subject from resolving with 3 successive recordings over the full 28-day study period, censoring will be applied, but the timepoint of censoring will depend on whether the last available recording indicates resolution or not. If the last recording indicates resolution, then censoring is at the first record of resolution from the last series of recordings of resolution of influenza symptoms. If the last recording does not indicate resolution, then censoring is done at the first scheduled timepoint after the last observation.

The size of the treatment effect will be estimated by the Kaplan-Meier estimate of median time to resolution of the 7 primary influenza-related symptoms in each treatment group. A Gehan-Wilcoxon test controlling for the stratification factors will be conducted to formally compare the time to resolution of the 7 primary influenza-related symptoms between pimodivir and placebo.

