5.3.1.3. Clinical outcomes

Measurement	Formula
Incidence of treatment-emergent adjudicated influenza complications	
The incidence of treatment-emergent adjudicated influenza complications from first intake of study drug until the end of the study will be categorized in a hierarchical fashion.
 
The overall category will consist of any complication.
 
The following subcategories are defined:
 
 ▪ Pulmonary complications: 
 • respiratory failure, • primary viral pneumonia, • secondary bacterial pneumonia, • exacerbations of chronic underlying pulmonary diseases, • bronchitis • other complications ▪ Extrapulmonary complications: 
 • Cardiovascular and cerebrovascular disease (eg, myocardial infarction, congestive heart failure, arrhythmia, stroke), • Muscular disorders (eg, myositis, rhabdomyolysis), • Central nervous system (CNS) involvement, • Acute exacerbation of chronic kidney disease, • Severe dehydration, • Decompensation of previously controlled diabetes mellitus, • Other infections (eg, sinusitis, otitis) • Other complications ▪ Pulmonary complications including sinusitis and otitis ▪ Major / minor complications ▪ Infectious / non-infectious complications 
The complications sinusitis and otitis are determined based on their MedDRA preferred terms as listed in Attachment 1, Table 6, for the protocol terms ‘Sinus infection’ and ‘Ear infection’ respectively. Only those terms that are judged to be complications by the adjudication committee will considered for the endpoint ‘pulmonary complications including sinusitis and otitis’.

Incidence of hospital admission 28 days after treatment initiation.	
Was the subject admitted to the hospital? The following medical encounters are considered as indicating hospitalization: ‘Emergency Room’, ‘Intensive Care Unit’, ‘Hospice/Palliative Care Unit’, and ‘Hospital Inpatient Department’. Subjects hospitalized for a preplanned surgery or procedure will not be counted as a hospitalized

	
subject for this endpoint. If a subject is discharged from hospital and subsequently readmitted, the subject will only be counted once as being admitted.
 
Categories will be Yes (1) or No (0).

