
Incidence of treatment-emergent adjudicated influenza complications including hospitalization
	
The incidence of treatment-emergent adjudicated influenza complications from first intake of study drug until the end of the study or hospitalization 28 days after treatment initiation as defined above.
 
Categories will be Yes (1) or No (0).

Time to resolution of fever (hours) [Time-to event]
	
It is assumed that all subjects will have fever at baseline.
 
The time to resolution of fever is defined as the time in hours from initiation of study treatment to the first of a successive series of 3 recordings for which the fever is resolved (see Table 8). The 3 successive recording may have been done over 4 scheduled successive analysis timepoints, in case of 1 missing in between timepoint.
 
In case the resolution of fever is not achieved, data will be censored.
 
Censoring will be done as follows:
 
 1) Last non-missing record(s) indicate resolution of fever (but insufficient recordings to meet the time to resolution) 
Censoring will be done at the first record of resolution of fever from the last series of recordings of resolution of fever
 2) Last non-missing record does not indicate resolution of fever 
Censoring will be done after the last observation, which is 08:00 on the same day if the last observation was a diary entry from 00:01 until 02:00, 20:00 on the same day if the last observation was a diary entry from 02:01 until 14:00, and 08:00 the next day if the last entry was a diary entry from 14:01 until 00:00.
 
Additionally, in the following cases the subject will be censored using a time-to equal to the maximum time across all subjects:
 
 ○ death, ○ if a subject had not resolved the fever at time of hospitalization and/or during hospitalization and no further data on fever resolution is available

Table 8: Resolution criterion for fever

Assessment	Resolution Criterion
Temperature	temperature as recorded on the ePRO device <37.0°C without the use of antipyretics on that day

The following ATC level 4 codes and generic medication names indicate an antipyretic medication:

- N02BA
- N02BE
- Ibuprofen
- Paracetamol
- Acetylsalicylic acid

If an antipyretic medication misses components of its start and/or stop dates (day and/or month and/or year) the following actions will be taken:

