5.3.2.3. Clinical Outcomes

Incidence of treatment-emergent adjudicated influenza complications, hospital admission rate, incidence of treatment-emergent adjudicated influenza complications including hospital admission, and incidence of all-cause mortality

The number and percentage of subjects in each parameter category and subcategory will be tabulated and listed. All subjects in the applicable analysis set will be counted for the denominator of the proportion.

The occurrence (yes/no) for hospital admission rate, incidence of treatment-emergent adjudicated influenza complications including hospital admission, and incidence of all-cause mortality will be analyzed using logistic regression as described above (Section 5.3.2).

The occurrence (yes/no) of influenza complications will be analyzed using logistic regression as described above, for each of the following categories:

- the overall influenza complications
- the pulmonary complications,
- the extrapulmonary complications
- the pulmonary complications including sinusitis and otitis
- the infectious complications
- the non-infectious complications
- the major complications
- the minor complications

Time to resolution of fever

Time to resolution of fever will be analyzed similarly as time to return to daily activities.

A subgroup analysis will be done based on the subset of subjects with fever at baseline (temperature $\geq 37.0^{\circ}\text{C}$) as recorded as part of the on-site vital signs assessment.

Temperature recordings made by the subject on the ePRO device lower than 34°C or higher than 43°C will not be included in the analysis.

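### The confirmatory hospital-admission endpoint has no rule for death, so a subject who dies within 28 days without a qualifying hospital encounter is scored as a non-event

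*Protocol*

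**What the plan says.** The protocol's Efficacy Analyses place "Hospital admission rates 28 days after treatment initiation" third in a fixed sequence, after the primary endpoint and influenza complications. Testing is "at the 2-sided 5% significance level". On method the protocol says only: "The incidence of hospital admissions 28 days after treatment initiation will be analyzed using a logistic regression", with the stratification factors as covariates.

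The scoring rule is in the SAP. Section 5.3.1.3 asks: "Was the subject admitted to the hospital? The following medical encounters are considered as indicating hospitalization". It then lists the emergency room, the intensive care unit, a hospice or palliative care unit, and the inpatient department. Preplanned surgery or procedures do not count, and the only categories are Yes (1) and No (0). Section 5.3.2.3 adds: "All subjects in the applicable analysis set will be counted for the denominator of the proportion". The Firth logistic model in 5.3.2 contains treatment and stratification factors only.

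The separate composite of adjudicated complications and hospitalization runs "until the end of the study or hospitalization 28 days after treatment initiation as defined above"; death is not named as a component. For the primary endpoint, SAP 5.2.2 says: "Missing recordings due to death or hospitalization are covered by using the maximum time over all subjects as the censored resolution time".

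**The concern.** Death prevents any later admission. If it is neither an event, an exclusion nor a stated intercurrent event, the endpoint gives its favourable score to the worst outcome. The distortion favours whichever arm has the unadmitted death: in the pimodivir arm it flatters the drug, and in the placebo arm it hides a failure of control.

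The study treats at-risk subjects aged up to 85 outside hospital, so a death with no hospital contact is possible. Because the test is confirmatory, a superiority claim would rest on a p-value that treats such a death as a good result. Mortality is analysed elsewhere, but that does not alter this p-value.

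**Working it through.** **1. Tracing the score.** Take a subject who dies on, say, Day 10 with none of the four encounter types.
- SAP 5.3.1.3: no qualifying encounter, so the answer cannot be Yes. There is no missing or death category, so it is No (0).
- SAP 5.3.2.3: the subject stays in the denominator.
- SAP 5.3.2: the model has no term for death.

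No sentence says that deaths are scored No. The result follows from these rules together.

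**2. Where a death rule exists.**

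| Endpoint | Rule for death |
|---|---|
| Primary, time to symptom resolution (SAP 5.2.1, 5.2.2) | Censored at the maximum time over all subjects |
| Other time-to-event endpoints (SAP 5.3.1) | Same |
| Hospital admission (SAP 5.3.1.3) | None |
| Complications including hospitalization (SAP 5.3.1.3) | None |
| All-cause mortality (SAP 5.3.1.3, 5.3.2.3) | Is the event; logistic regression, outside the confirmatory sequence |

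**3. Size.** Neither document gives an admission rate, death rate, effect size or power for this endpoint, so there is no figure to reproduce. What follows is an illustration with assumed counts.

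Inputs: 720 subjects (protocol 11.3) and about 15% not confirmed as influenza A (same section). Subjects per arm in the ITT-i set: n = 720 × 0.85 / 2 = 306.

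Test: unstratified Firth logistic regression. With one binary covariate, its estimate is the log odds ratio after adding ½ to each cell. For e_t events on pimodivir and e_c on placebo:
- log OR = ln[(e_t + ½)/(n − e_t + ½)] − ln[(e_c + ½)/(n − e_c + ½)]
- SE = √[1/(e_t + ½) + 1/(n − e_t + ½) + 1/(e_c + ½) + 1/(n − e_c + ½)]

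For 14 admissions on placebo against 5 on pimodivir: log OR = ln(5.5/301.5) − ln(14.5/292.5) = −1.000; SE = √(1/5.5 + 1/301.5 + 1/14.5 + 1/292.5) = 0.508; z = −1.97; two-sided p = 0.049.

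In the second row of each pair, one unadmitted pimodivir death is recoded as an event.

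| Placebo vs pimodivir | log OR | SE | z | p |
|---|---|---|---|---|
| 14 vs 5 | −1.000 | 0.508 | −1.97 | 0.049 |
| 14 vs 6 | −0.829 | 0.479 | −1.73 | 0.083 |
| 20 vs 6 | −1.196 | 0.458 | −2.61 | 0.009 |
| 20 vs 7 | −1.050 | 0.435 | −2.42 | 0.016 |

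Taking the SE from the fitted model's information matrix instead gives 0.084 for 14 vs 6 and does not change the other p-values as shown. The stratification and the inverse-normal combination of pre- and post-interim data (SAP 5.1.1) are not applied here.

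**4. How many deaths.** If 28-day mortality were between 0.1% and 0.5% (assumed), the 612 ITT-i subjects would yield 612 × 0.001 = 0.6 to 612 × 0.005 = 3.1 deaths in both arms together. Only those without a qualifying encounter are affected.

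**The case against.** The strongest reply is that the gap touches very few subjects and that other analyses would reveal the deaths. Much of this stands.

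- A reader might infer that every death outside an inpatient ward, or before formal admission, is scored as a success. The documents do not support that. Emergency room and hospice or palliative care encounters count as hospitalization, so a subject who dies in either is scored Yes.
- A reader might infer that fatal events escape the confirmatory sequence, or the composite, because neither names death. That goes too far. A fatal event adjudicated as an influenza complication counts at the preceding step and in the composite, whether or not the subject was admitted. Admission is tested only if that step succeeds. Whether a given death qualifies depends on adjudication, and it remains 0 on the admission endpoint.
- A reader might infer that mortality is only tabulated. It is a named secondary endpoint, analysed by logistic regression. It lies outside the alpha-controlled sequence, so it informs interpretation without correcting the admission test.
- A reader might infer that one death would commonly overturn the result. A pooled two-proportion z-test moves 14 vs 5 from p = 0.036 to 0.069, which looks like a fall from a comfortable result. That is not the planned model. Under the unstratified Firth test the example starts at 0.049, on the threshold, and the 20 vs 6 example does not change its conclusion.
- The earlier community study had no deaths (protocol 1.1). It enrolled adults with uncomplicated influenza, so it offers limited reassurance for this at-risk population.

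The contrast with the primary endpoint can also be discounted, since a time to recovery needs a rule once recovery can no longer be observed. But that does not supply a rule for the admission endpoint. What remains is a scoring rule that, in a small group, points the wrong way on a confirmatory endpoint.

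**Conclusion.** The point holds in a limited form. As written, a subject who dies within 28 days with none of the four encounter types is scored as a non-event on the third confirmatory endpoint, and no other text in either document changes that. The bias favours the arm with the death. With no such deaths, nothing changes.

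The size cannot be determined from the documents. Under the assumed counts, a single recoded pimodivir death changes the conclusion only when the result is already marginal. That rests on 306 subjects per arm, an unstratified test and the death falling in the pimodivir arm. The documents do not support a claim that the confirmatory result would be materially driven by deaths. This should be corrected because the correction is cheap and better made before anyone knows which arm the deaths are in.

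**What to change.** Before unblinding, in SAP 5.3.1.3:
- score the endpoint Yes (1) for hospital admission or death from any cause within 28 days of treatment initiation;
- add death to the composite of complications and hospitalization;
- keep admission alone as a supportive analysis.

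Align the objective, endpoint and testing-sequence wording in the protocol (synopsis, 2.1, 11.4) and the SAP (1.1, 5.1.1), and check where the endpoint is reused in the subgroup and PK/PD sections (SAP 2.3, 9.2).

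If the sponsor prefers to keep admission alone as the confirmatory endpoint, state the strategy for death explicitly. Prespecify a sensitivity analysis of the confirmatory test, with the same model and combination rule, that scores death without admission as Yes.

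Cost: no new data, since deaths are already collected and analysed. The endpoint would no longer be pure admission, and the wording changes reach several sections. Timing matters too: the current SAP amendment is dated 1 July 2020 and the interim cohort was randomized by 28 February 2020, so a late redefinition must be documented as made blind to treatment. The sensitivity analysis avoids redefining the endpoint, but leaves the confirmatory p-value as it is.

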### ***Exploratory Endpoints***

Time to resolution of impact of influenza on daily activities, emotions, and others, as defined by the Flu-iiQ™ questionnaire (Modules 2, 3, and 4), is the time at which all scores within each module are reported as “no difficulty” (Module 2), “not at all” (Module 3), and “not at all concerned” (Module 4), respectively, and will be analyzed analogously to the primary endpoint. Each module will be evaluated separately.

### ***Other Analyses***

Descriptive statistics by day of assessment will be provided for PGIS and PGIC questionnaires. The EQ-5D total scores and EQ-5D visual analog scale (VAS) ‘thermometer’ scores will be evaluated at each time point.

The PGIS and PGIC questionnaire responses may be used as anchors to perform responder analyses for selected PROs. The anchor-based analysis, if performed, will be defined and described in a separate report.

For the EQ-5D questionnaire a post-hoc analysis plan will be developed when the economic model structure is finalized, and results of this analysis will be reported separately.

### **Resistance Analyses**

Development of resistance against pimodivir (and other antivirals in the SOC if applicable) will be determined by viral sequencing and phenotypic testing. All baseline samples as well as the last evaluable post-baseline samples will be analyzed. Additional genotypic and phenotypic testing might be requested by the sponsor virologist.

The presence of baseline polymorphisms potentially affecting virologic response will be analyzed. The incidence of emerging mutations as well as changes in drug susceptibility (fold change in 50% of the effective concentration [EC50] value) will be described and compared between treatment arms. Results of the resistance analysis may be reported in a separate report.

